1.0 Study Summary

Study Title	Feasibility of Screening, Brief Intervention for HIV+ Adults 50+ in Primary Care Settings
Study Design	We will use a repeated measures randomized control trial design to compare patient outcomes at baseline as well as 3 and 6 months post-intervention.
Primary Objective	Feasibility and Acceptability of intervention
Secondary Objective(s)	Substance misuse
Research Intervention(s)	Screening, Brief Intervention, Referral to Treatment with Peer Navigator (SBIRT-PN)
Study Population	HIV+
Sample Size	90
Study Duration for individual participants	6 months
Study Specific Abbreviations/ Definitions	SBIRT-PN = Screening, Brief Intervention, Referral to Treatment with Peer Navigator

2.0 Objectives*

In order to develop effective substance use intervention models for HIV care settings the specific aims of the current project are:

Aim1: Examine the feasibility of implementing the SBIRT-PN model in Infectious Disease-Medical Specialties Clinics in the state of Florida.

H1: We hypothesize that the SBIRT-PN model will demonstrate high feasibility as evidenced by at least 80 % of the total N having screenings.

Aim2a: Assess the acceptability of SBIRT-PN.

H2a: We hypothesize that SBIRT-PN will demonstrate high acceptability among patients enrolled in this condition.

Aim2b: Assess the acceptability of SBIRT-PN among HIV-positive individuals by age cohort (younger vs older).

H2b: We hypothesize that SBIRT-PN will demonstrate higher acceptability among older HIV-positive patients enrolled in this condition.

Aim3: Assess influence of SBIRT-PN model on treatment engagement and substance use compared to enhanced treatment as usual (TAU).

H3: We hypothesize that those in the SBIRT-PN condition will evidence greater treatment engagement and a reduction in substance use.

3.0 Background*

Substance use science-to-service gap needs to close for the underserved aging with HIV. Many effective interventions do not translate into meaningful outcomes that improve patient care. Therefore, NIDA and the Office of AIDS Research have prioritized research that promotes the uptake of evidence-based interventions into real-world settings. In order to provide effective patient-centered care, effective interventions need to reach those in need. In particular, substance use interventions have lagged in moving from the bench (research labs) to the community (real-world settings). Extant literature suggests that peer navigators may improve treatment engagement among substance users and thereby has the potential to improve the effectiveness of SBIRT in this population in particular.

Florida provides the opportunity to implement substance use interventions among older HIV-positive adults. In Florida 42% of people living with HIV are aged 50 years and older compared to 31% in the rest of the United States. While cART has transformed HIV into a manageable chronic condition, leading to a large population aging with the disease, people aging with HIV continue to engage in high risk behaviors. At this stage in the HIV epidemic, we must use available evidence-based tools to meet the needs of those aging with HIV. Older adults living with HIV misuse alcohol and illicit drugs at rates higher than the general population. In addition, HIV+ adults aged 50 years and older are likely to be frailer than their chronological age indicates due to their

PROTOCOL TITLE: Feasibility of Brief Intervention for HIV+ Adults 50+ in Primary Care Settings

disease status, which makes them more vulnerable to the consequences of substance misuse (i.e., greater intoxication even with lower levels of consumption). Further, substance misuse is associated with decreased medication adherence, decreased engagement in HIV care, more medical co-morbidities, higher rates of depression, and poorer quality of life. Extant research suggests depression and pain are considered motivators of misuse and may make patients less responsive to interventions.

Importantly, depressive symptoms among older, chronically ill populations are associated with transition from informal community-based care by family and friends to institutionalization. Therefore, studies located in Florida provide an opportunity to examine how primary care health systems can adopt interventions to reach this population and remain effective.

Determine best methods for improving uptake of substance use interventions in real-world settings While the primary care setting presents an opportunity to address substance misuse among older HIV-positive adults, barriers exist at multiple levels in the public health sector. Extant literature indicates that underserved adults aging with HIV need substance use intervention on a broad scale. However, to be effective we need to improve our understanding of the mediators and moderators of effective delivery of substance use interventions in this population. A study that implements SBIRT-PN and then examines the barriers to uptake will provide data needed to implement evidence-based substance use interventions in public health settings while creating sustainable interventions that the community can maintain

4.0 Study Endpoints*

Primary Outcome

Feasibility Calculation. Feasibility is defined as the extent to which the intervention can be successfully used or carried out within the UF Health Infectious Disease-Medical Specialties Clinic. Therefore, we will calculate feasibility using the following steps (see link to method for calculation below):

- **Step 1:** Enumerating all potential participants in target population. The target population will be defined as all patients seen by [name] seen during study period.
- **Step 2:** Quantify Exclusions. List reasons for and number of exclusions.
- **Step 3:** Quantify missed cases. List number of lost cases or missed due to lack of staff resources, etc.
- **Step 4:** Quantify Eligible Participants. List number of known eligible participants who were offered participation.
- **Step 5:** Quantify number of Patients Reached. Divide number of participants enrolled to determine percent participation.
- **Step 6:** Report most common reasons for declining participation.

<http://re-aim.org/resources-and-tools/calculations/calculating-and-reporting-on-reach/>

Acceptability Questionnaire. This 10-item questionnaire (1 = not acceptable to 5 = highly acceptable) queries the participant on the acceptability of the program. Item content includes the following:

PROTOCOL TITLE: Feasibility of Brief Intervention for HIV+ Adults 50+ in Primary Care Settings

1. Program was a good use of my time
2. Program was helpful
3. Program will be useful in my daily
4. Likeability of interventionist
5. Clinical skill of interventionist
6. Likeability of assessor
7. Ease of participation in assessments
8. Ease of participation in intervention
9. Interactions with program staff
10. Overall rating.

To examine ratings of acceptability, we will use the overall acceptability score and percentage of acceptability. Overall acceptability will be assessed by summing ratings from the 10-item questionnaire to provide a total intervention acceptability score for the intervention, such that acceptability scores for the intervention could range from 10 (low acceptability) to 50 (high acceptability). The intervention will be considered to have acceptability if 80% of the participants rank the intervention as acceptable (i.e., 4 or higher) on 80% or more of the scale items. We will then examine each question of the Acceptability Questionnaire separately to determine strengths and weaknesses of the intervention.

Secondary Outcomes

Substance Use Treatment Engagement: Participants will self-report if they obtained formal substance use treatment (i.e., any services sought to address substance use from individual therapy to 12 step fellowships). We will request treatment facility information and permission to verify treatment. Once treatment has been verified, treatment engagement will be coded as 0= no formal treatment 1= formal treatment engagement

Substance use NIDA STTR Drug and Alcohol Use Measure: A standard measure from the NIDA STTR Vulnerable Populations Data Harmonization tool kit will be used. It will assess quantity and frequency of types of substances used in the prior 30 days.

Biologically Confirmed Drug Use: A CLIA 12-Panel Instant Drug Test Cup (CLIAwaived™, San Diego, CA), which tests for the presence of 12 common substances in the urine will be used.

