5.0 Study Intervention

Intervention Procedures: The 30 minute intervention session will cover the following content: 1) Psycho-educational content (5 minutes): The interventionist will discuss substance use and misuse, HIV, and the interaction of aging and substance use (e.g. greater intoxication effects with lower amounts). 2) Readiness Assessment (10 minutes): The interventionist will give the patient feedback on their NM-ASSIST score and assess the patient's readiness to change based on Prochaska's stages of change. 3) Goal-Setting (5 minutes): The interventionist will use motivational interviewing techniques to identify the patients' most salient reasons for addressing substance use issues. 4) Identifying and prioritizing needs (5 minutes): The interventionist will use problem-solving techniques to help patients identify which services may best help them work

PROTOCOL TITLE: Feasibility of Brief Intervention for HIV+ Adults 50+ in Primary Care Settings

towards their goals. Services will include (but are not limited to) emergency crisis services, counseling to deal with substance use, referral to local self-help groups (Alcoholics Anonymous, Narcotics Anonymous, etc.), legal assistance, faith-based counseling, or mental health counseling. 5) Assignment of Peer Navigator and Session wrap (5 minutes): The interventionist will use a referral resource guide to provide the contact information of agency representatives and help the patient formulate a plan for follow-up.

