10.0 Subject Population*

Participants will be 90 patients recruited through DOH Columbia County and CAN Community Health.

Study inclusion criteria includes that patients must be:

1. HIV-positive (seropositive confirmed by medical records).
2. Arrive for a clinic visit with an HIV physician.
3. Have a substance misuse screening score indicating moderate or high risk.

Persons will be ineligible if they:

1. are unable to interview and consent in English
2. unwilling or unable to participate in follow up
3. currently in addiction treatment
4. have a medical marijuana prescription

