25.0 Resources Available

Since SBIRT is intended to be a universal intervention within a targeted setting, all adults (18+) who are being seen in clinic will be screened using validated screening instruments as part of routine care. Scores and the nature of the follow up (i.e., referred to brief intervention or no intervention needed) will be documented in the electronic medical record. We will train all recruiters and clinic staff to provide an extensive explanation of why we are offering these services, as the patients may not perceive themselves as having a substance misuse issue.

Universal Screening Procedures

Screening is intended to identify individuals at varying levels of risk associated with the use of alcohol and/or drugs. It is not intended to provide a formal diagnosis (which is the function of clinical assessment), but rather to provide guidance for deciding which level of intervention may be needed to address the identified level of risk. The ASSIST is an eight-item instrument developed by the World Health Organization (WHO) to screen for hazardous, harmful, and dependent use of alcohol, tobacco, and drugs. The ASSIST typically takes about 5-10 minutes to administer, although it can take longer depending on the number of drugs used over the lifetime. For each drug endorsed, questions are asked about frequency of use, problems related to use, dependence indicators, and injection drug use in the three months prior to the current administration of the instrument. Following ASSIST administration, separate risk scores are calculated, with scores falling within a low-, moderate-, or high-risk range. Table 1 shows the risk-level scores for alcohol and drugs and the indicated intervention for each risk level, as specified in the WHO brief intervention manual. We will use a computer based version of the ASSIST to make the screening faster to administer and score (see link below).

<https://www.drugabuse.gov/nmassist/>

Table 1 ASSIST risk scores and level of intervention

	ASSIST Alcohol Score	Assist Drug Score	Intervention
Low Risk	0 – 10	0 – 3	Feedback on ASSIST score, literature
Moderate Risk	11 – 26	4 – 26	Feedback on ASSIST score, literature, brief intervention
High Risk	27+	27+	Feedback on ASSIST score, literature, brief intervention, referral to treatment

Retention

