Our first step will be to see if the intervention influenced formal engagement in substance use treatment. Using chi-square analyses we will examine group difference on engagement in formal treatment (0=no treatment/1=treatment confirmed). To test the remainder of the hypothesis, analyses will rely on mixed model repeated measures ANOVA since the relatively small sample size is likely to prohibit more sophisticated statistical modeling. Hypotheses testing rely on inspection of F values and associated p values. A mixed model ANOVA is used to test for differences between two or more independent groups while subjecting participants to repeated measures. In the current analyses the fixed effect will be group condition (SBIRT-PN or TAU) and the random effect will be number of drug use days in the past 3 and 6 months.

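### The chi-square for treatment engagement ignores site and screening risk level, both known before randomisation; a stratified test is a cheap, modest gain in precision

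*Protocol*

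**What the plan says.** Protocol section 10.0 admits patients who "Have a substance misuse screening score indicating moderate or high risk". Section 4.0 defines engagement broadly, as "any services sought to address substance use from individual therapy to 12 step fellowships", and codes it alike for everyone: "treatment engagement will be coded as 0= no formal treatment 1= formal treatment engagement".

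The test is the same in Protocol section 17.0 and in the SAP under Aim 3: "Using chi-square analyses we will examine group difference on engagement in formal treatment". Neither names a stratification factor. Protocol section 6.0 randomises in blocks of four within each recruitment site.

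Two places describe what participants at each risk level are offered:

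- Table 1 in Protocol section 25.0, given "as specified in the WHO brief intervention manual", lists "Feedback on ASSIST score, literature, brief intervention, referral to treatment" for high risk. The moderate-risk row stops at brief intervention.
- Protocol section 5.0 describes one study session. It covers counselling for substance use, self-help referral, a resource guide and assignment of a peer navigator, and attaches no risk condition to any of these.

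**The concern.** Two facts fixed before randomisation are left out of the engagement test. Site is a design factor, so an analysis that ignores it does not follow the randomisation. Risk level is likely to predict who enters formal treatment, whichever arm they are in. Randomisation does not balance it, so any chance difference between arms in the high-risk share goes straight into the pooled comparison as noise.

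The plan also undertakes to control for baseline variables that differ between arms before testing each secondary outcome. A plain two-by-two chi-square has no means of doing that, so the undertaking cannot be kept for engagement as written.

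At stake is precision in a trial of 90, and the ability to interpret the result. Without engagement by arm within risk level, a reader cannot tell whether the overall figure reflects similar effects at both levels or an average of different ones. The disagreement between Table 1 and section 5.0 adds to this, because it leaves open what a moderate-risk participant in the SBIRT-PN arm is offered.

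**Working it through.** The documents give no engagement rates, effect size, power or high-risk share, so there is no design figure to reproduce. Everything below except N is assumed.

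**Inputs.** N = 90 (Protocol 10.0), so 45 per arm. Maximum dropout 20% (Protocol 25.0), so 36 per arm. Two-sided alpha .05 is assumed. The high-risk share at entry is h, assumed between 0.2 and 0.7.

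**1. Why stratifying helps, and why only modestly.** Within an arm, the variance of a binary outcome splits into a part within risk levels and a part between them. The between part is h(1−h)d², where d is the gap in rates between high and moderate risk. Take h = 0.5:

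- Rates of 20% and 5%: mean 0.125, total variance 0.125 × 0.875 = 0.1094, between part 0.25 × 0.15² = 0.0056. Share: 5.1%.
- Rates of 45% and 5%: mean 0.25, total variance 0.1875, between part 0.25 × 0.40² = 0.04. Share: 21.3%.

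Stratification removes the between part, so the gain depends on how strongly risk level predicts engagement.

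**2. Simulated power, risk stratum only.** With 45 per arm, 20% v 45% at high risk and 5% in both arms at moderate risk:

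| h | Pooled chi-square | CMH by risk level |
|---|---|---|
| 0.7 | 50.7% | 52.9% |
| 0.5 | 34.6% | 36.9% |
| 0.3 | 19.2% | 20.0% |
| 0.2 | 13.1% | 12.5% |

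The change runs from −0.6 to +2.3 points.

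**3. Simulated power, site and risk strata.** With 45 per arm, risk level prognostic and site shifts of ±0.5 on the log-odds scale, the stratified test kept type I error at about 5% or below. It raised power by about 1 to 17 points over the pooled test. Most scenarios fell between 1 and 7; the larger gains need a strongly prognostic risk level.

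**4. Does pooling weaken the effect?** That depends on the moderate-risk effect, which is unknown. Assume 10% v 40% at high risk, 10% in TAU at moderate risk, and h = 0.5. Power = Φ{[Δ√n − 1.96√(2p̄(1−p̄))] / √(p₁(1−p₁) + p₂(1−p₂))}.

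- No effect at moderate risk: pooled rates are 10% v 0.5 × 40% + 0.5 × 10% = 25%, so Δ = 0.15. Power = Φ[(1.006 − 1.053)/0.527] = Φ(−0.09) = 46.4%. CMH by risk level: 47.8% by simulation.
- Same effect at both levels: Δ = 0.30. Power = Φ[(2.012 − 1.200)/0.574] = Φ(1.41) = 92.1%.
- High risk only (22 per arm): Power = Φ[(1.407 − 1.200)/0.574] = Φ(0.36) = 64.1%, whichever case holds at moderate risk.

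At 36 per arm the first two become 38.6% and 85.2%. The stratified test recovers almost none of the power lost when moderate-risk participants do not respond; that is not what it is for.

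**5. Width of the within-level estimates.** With 20% v 45%, the 95% half-width is 1.96√[(0.16 + 0.2475)/n]. With 22 per arm this is ±27 points; with 14 per arm (h = 0.3), ±33 points.

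**The case against.** A reader might go further and infer that pooling dilutes the effect H3 predicts, because Table 1 refers only high-risk patients, and that H3 should therefore be judged in the high-risk group. The documents do not support this, for three reasons.

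- H3 is stated for the whole SBIRT-PN condition. In a mixed population the pooled difference is the average effect H3 describes.
- Section 5.0 offers referral content and a navigator without a risk condition, and the endpoint counts 12-step fellowships. A moderate-risk participant can therefore be steered to a service that scores 1.
- Enhanced TAU is not described, so it is unknown whether high-risk controls are referred as well.

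Restricting to high risk is also a poor trade. It helps only if moderate-risk participants respond little or not at all, and it cuts power from 92.1% to 64.1% in the equal-effect example.

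It can also be said that stratifying a secondary test in a feasibility pilot is a matter of preference and gains little. The second half of that stands: where risk level predicts little, the gain is nil or fractionally negative. But the change uses factors already known for every participant, one of them already built into the randomisation, and it gives the test the adjustment the plan promises.

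**Conclusion.** The concern holds as a point about efficiency and clarity, not validity. The pooled chi-square is a legitimate test of the engagement part of H3, but it leaves out a design factor and a probable predictor that are available at no cost. The expected gain is modest: about 1 to 7 power points in most assumed scenarios, more if risk level is strongly prognostic, and near zero if it is not. These figures rest on 45 per arm, two-sided .05 and engagement rates and risk shares that the documents do not supply.

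The contradiction between Table 1 and section 5.0 stands regardless of any assumption and must be reconciled. Until it is, whether the effect should be smaller at moderate risk is an open question. A null overall result should be read in that light, not explained away by an assumed dilution.

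**What to change.** In SAP Aim 3, with matching wording in Protocol section 17.0:

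1. Replace the chi-square for engagement with a Cochran-Mantel-Haenszel test stratified by recruitment site and screening NM-ASSIST risk level (moderate or high). Keep it as the single overall engagement test for H3, in all randomised participants.
2. Report the risk split by arm, and engagement by arm within each risk level, as descriptive estimates with confidence intervals and no separate tests.
3. State that the H3 conclusion is not drawn from the high-risk subgroup.
4. Reconcile Table 1 with section 5.0 on whether referral to treatment applies to moderate-risk SBIRT-PN participants.

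Items 1 to 3 are changes of wording; no new data are needed. The cost is small cells. With equal sites and h = 0.3, for example, 90 × 0.3 / 2 = 13.5 high-risk patients per site, or about 7 per arm, and the within-level intervals will be wide.

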5.0 Study Intervention

Intervention Procedures: The 30 minute intervention session will cover the following content: 1) Psycho-educational content (5 minutes): The interventionist will discuss substance use and misuse, HIV, and the interaction of aging and substance use (e.g. greater intoxication effects with lower amounts). 2) Readiness Assessment (10 minutes): The interventionist will give the patient feedback on their NM-ASSIST score and assess the patient's readiness to change based on Prochaska's stages of change. 3) Goal-Setting (5 minutes): The interventionist will use motivational interviewing techniques to identify the patients' most salient reasons for addressing substance use issues. 4) Identifying and prioritizing needs (5 minutes): The interventionist will use problem-solving techniques to help patients identify which services may best help them work

PROTOCOL TITLE: Feasibility of Brief Intervention for HIV+ Adults 50+ in Primary Care Settings

towards their goals. Services will include (but are not limited to) emergency crisis services, counseling to deal with substance use, referral to local self-help groups (Alcoholics Anonymous, Narcotics Anonymous, etc.), legal assistance, faith-based counseling, or mental health counseling. 5) Assignment of Peer Navigator and Session wrap (5 minutes): The interventionist will use a referral resource guide to provide the contact information of agency representatives and help the patient formulate a plan for follow-up.

6.0 Procedures Involved*

Recruitment/Sampling: Patients will be recruited using convenience sampling technique from HIV primary care clinics with whom the PI works regularly: the Columbia County Department of Health (Lake City, FL) and the CAN Community Health Clinic (Jacksonville, FL)

Preliminary Screen: Patients will be prescreened for eligibility using a computerized screening tool, NIDA Modified Alcohol, Smoking, Substance Involvement Screening Test [NM-ASSIST], to assess substance misuse risk level. All clinic patients will have the opportunity to complete the substance use screening assessment after checking in for their appointment. All who score moderate and above on the alcohol or illicit substance portion of the NM-ASSIST and meet eligibility criteria will be referred to the study. We will train all recruiters (clinic staff) to provide an extensive explanation of why we are offering these services, as the patients may not perceive themselves as having a substance misuse issue.

Baseline Assessment Procedures: Following a successful initial screen, study staff will explain the procedures of the study and obtain informed consent. All study activities will be conducted in a private room in the clinic. The research assistant (RA) performing the assessment will verify the patient's complete understanding of the informed consent form and all study procedures. Following informed consent, patients will complete the baseline assessment. The baseline assessment will consist of urine drug screen and a series of research questionnaires delivered on a mobile device. The research questionnaires include information on: substance use, substance use treatment, HIV treatment engagement, depression, and pain. The assessment is relatively brief in order to maximize willingness to participate and decrease patient burden. The assessment will take approximately 30 minutes to complete. The questionnaires will be given in a computerized. The iPad/tablet will use REDCap survey software, which provides direct, encrypted transfer of information via internet to a secure study server.

Three and Six Month Follow-Up Assessment: *Participants will be contacted three and six months post-intervention to schedule an in-person follow-up assessment. We will evaluate substance use treatment engagement post intervention and substance use (self-report and urine toxicology analysis). Participants will be compensated \$30 for each*

Randomization: We will use Block random assignment (blocks of 4 by each recruitment site) to ensure equal numbers are assigned to each condition by site. Randomization should create groups with equal characteristics with respect to disease related and medical variables. However, we will assess for baseline differences prior to conducting any analyses and control as necessary.

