To examine ratings of acceptability, we will use the overall acceptability score and percentage of acceptability. Overall acceptability will be assessed by summing ratings from the 10-item questionnaire to provide a total intervention acceptability score for the intervention, such that acceptability scores for the intervention could range from 10 (low acceptability) to 50 (high acceptability). The intervention will be considered to have acceptability if 80% of the participants rank the intervention as acceptable (i.e., 4 or higher) on 80% or more of the scale items. We will then examine each question of the Acceptability Questionnaire separately to determine strengths and weaknesses of the intervention.

Aim 2a and 2b (Acceptability): Acceptability scores will be calculated for all participants as listed above to determine overall acceptability of the SBIRT model. Sub analyses will be conducted for disease type and HIV x age using calculations listed above. Acceptability will be examined by disease type HIV vs. non-HIV. Acceptability will also be examined for HIV only by younger (≤ 49) versus older (≥ 50).

Aim 3: We will clean the data, examine variable distributions, compute descriptive statistics, examine outliers, and examine the effectiveness of randomization prior to analyses of specific aims to ensure the underlying assumptions of normality and equal variance have not been violated. Before testing each secondary outcome, we will examine whether intervention and control group participants differ on potential confounding variables at study entry. We will control for a variable if it differs by condition on the outcome variable being tested in that analysis at $p < .05$. Using chi-square (or t-test for continuous variables) we will examine the associations between the dependent variables and relevant demographic variables. All analyses will employ an intent-to-treat approach.

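### Patients can enter on alcohol risk alone, but the Aim 3 model names only drug use days, in a window that taken literally the 30-day measure cannot supply, and calls that outcome a random effect

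*Protocol*

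**What the plan says.** **Entry.** Protocol 6.0 (Preliminary Screen) refers to the study "All who score moderate and above on the alcohol or illicit substance portion of the NM-ASSIST", provided the other criteria are met; 13.0 repeats this. Table 1 in 25.0 scores the two separately: moderate risk starts at 11 for alcohol and at 4 for drugs. Inclusion criterion 3 in 10.0 asks for moderate or high risk without restricting it to drugs.

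**Target.** The background (3.0) puts the two together: "Older adults living with HIV misuse alcohol and illicit drugs at rates higher than the general population". H3 in 2.0 reads: "We hypothesize that those in the SBIRT-PN condition will evidence greater treatment engagement and a reduction in substance use".

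**Measurement.** Among the secondary outcomes in 4.0 is the NIDA STTR Drug and Alcohol Use Measure: "It will assess quantity and frequency of types of substances used in the prior 30 days". Section 6.0 has self-reported substance use assessed at the three- and six-month visits.

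**Analysis.** The Aim 3 text in Protocol 17.0 and in the SAP is the same on this point. Treatment engagement is compared by chi-square. For the rest: "To test the remainder of the hypothesis, analyses will rely on mixed model repeated measures ANOVA". The final sentence makes group condition the fixed effect and then says "the random effect will be number of drug use days in the past 3 and 6 months". Neither document names another substance-use variable for this model.

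**The concern.** The variable in the model differs from the measured outcome in three ways.

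- It speaks of drug use days, while patients may enter on alcohol, the hypothesis is about substance use, and the instrument covers both.
- It speaks of the past 3 and 6 months, while the instrument asks about 30 days.
- It is given the role of random effect, so the sentence does not identify any dependent variable.

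If the sentence is followed as written, a participant who entered because of drinking contributes no alcohol result to the model meant to test H3. If it is not followed as written, the analyst must decide whether alcohol counts, whether it is combined with drugs or kept apart, and what period applies. Nothing in the plan prevents those decisions from being made after the data are seen.

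**Working it through.** The documents give no effect size, standard deviation or power calculation for Aim 3, so there is no stated figure to reproduce. The check is a comparison of texts plus one piece of arithmetic.

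**1. Can someone enter on alcohol alone?** Yes. The referral rule joins the alcohol and illicit-substance portions by *or*, and Table 1 gives each its own cut-off. A patient with an alcohol score of 11 or more and a drug score of 0 to 3 meets the screening rule.

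**2. Does the named variable include alcohol?** The text does not say. Section 25.0 once uses *drug* generically when describing the screening questions. Elsewhere the two are kept apart: in the name of the outcome measure in 4.0, in the two columns of Table 1, and in the description of what the screening tool covers. Even if alcohol is included, it is not stated whether its days are pooled with drug days or analysed separately. Those are different endpoints.

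**3. Can the named window be derived from the measure?** Inputs: recall of 30 days (4.0); 3 months = 365.25/4 = 91.3 days; 6 months = 365.25/2 = 182.6 days.

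- One recall against 3 months: 30/91.3 = 32.9%.
- One recall against 6 months: 30/182.6 = 16.4%.
- Both follow-up recalls against 6 months: 60/182.6 = 32.9%, leaving 182.6 − 60 = 122.6 days never asked about.

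These figures apply only if a 3- or 6-month day count is really meant. If the phrase means 30-day recall taken at the month 3 and month 6 visits, the shortfall is zero.

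**4. What role does the variable have?** In a repeated-measures comparison of two arms, drug use days are the response. A random effect would normally be the participant, to account for repeated observations on the same person. The sentence also omits time and the condition-by-time interaction, although Protocol 17.0 describes measurements at baseline and two follow-ups.

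**5. Dilution.** Let f be the share who entered on alcohol alone, taken as equal in the two arms, D1 the mean drug-days difference between arms among the others, and D2 the same difference among alcohol-only entrants. The overall difference is (1 − f) × D1 + f × D2. If the intervention does not change drug use in alcohol-only entrants, D2 = 0 and the contrast shrinks to (1 − f) × D1. The documents give none of f, D1 and D2, so the direction can be stated under that condition but the size cannot.

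**The case against.** The strongest reply is that this is loose wording around a sensible intention, and much of it stands.

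**Window.** The Aim 3 text in Protocol 17.0 opens by describing a repeated-measures design with a baseline and follow-ups at 3 and 6 months, and the summary in 1.0 says the same. In that context the phrase most naturally refers to the visits. A reader might infer that the trial will lack most of the data its model needs; the documents do not support that. The SAP, however, omits that design description and never mentions the 30-day measure, so a reader of the SAP alone has only the faulty sentence.

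**Alcohol.** A reader might infer that the trial ignores alcohol or has no intention of testing it. That goes too far. The instrument collects alcohol use, and both documents show intent to test every secondary outcome: "Before testing each secondary outcome, we will examine whether intervention and control group participants differ on potential confounding variables at study entry". Participants who entered on alcohol risk also count in the treatment-engagement comparison, since 4.0 defines engagement as any service for substance use, including 12-step groups. What remains is narrower: the intent is stated, but the variable that would carry it out is not.

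**Loss of power.** A reader might want a percentage for the dilution. Any such figure would rest wholly on an assumed share of alcohol-only entrants. Nor is (1 − f) a true bound, because an effect in the opposite direction in that group would shrink the contrast further. Some drug use in that group would not by itself lessen the dilution; only an intervention effect on that use would.

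**Remedy.** H3 does not require two outcomes, and a single variable for days of any substance use could also serve it. That is fair, but the plan would still have to say so.

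**Conclusion.** The point holds in limited form and should be fixed. Two defects do not depend on how the window is read: alcohol has no defined place in the only substance-use model, although alcohol risk alone admits patients, and the outcome is labelled a random effect. The third is conditional. Taken literally, the window exceeds what the measure can supply, with coverage of about 33% of 3 months or 16% of 6 months per recall; read as visit times, it is an error of wording only.

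The consequence is an undefined secondary analysis, with room for choices after the data are seen. Dilution of a drug-days contrast is possible but cannot be sized from the documents. Aim 3 is secondary, alcohol data are collected in any case, and the primary feasibility and acceptability aims are not affected.

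**What to change.** In the Aim 3 text of Protocol 17.0 and of the SAP, replace the last sentence (the one assigning fixed and random effects) with:

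> The dependent variables will be days of drug use in the prior 30 days and, separately, days of alcohol use in the prior 30 days, each measured at baseline, month 3 and month 6; condition, time and condition-by-time will be fixed effects and participant the random effect.

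This settles the alcohol question, the window and the role of the variable together. It assumes that the instrument yields days of use by substance; 4.0 says only that it records quantity and frequency by type, so this should be confirmed first.

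The cost is one sentence in each document and two derived variables, with no new visit or assessment. The downside is two modelled self-report outcomes instead of one in a 90-person pilot. Both should be labelled exploratory.
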